## ABSTRACT

In the United States, patients dependent upon parenteral nutrition (PN) receive parenteral fat emulsions composed of soybean oils. Lipids are necessary in PN-dependent patients due to their high caloric value and essential fatty acid content. They have been implicated in predisposing patients to PN-associated liver disease, and children requiring prolonged courses of PN are at risk for developing PN-associated liver disease. Animal studies have shown that IV fat emulsions such as fish oil that are high in eicosapentaenic and docosahexaenoic acid reduce impairment of bile flow which is seen in cholestasis caused by conventional fat emulsions. We hypothesize that a fat emulsion comprised of omega-3 fatty acids (i.e., fish oil) such as Omegaven™ will be well tolerated and will reduce the inflammatory effect in the liver of prolonged PN exposure, with the potential of reversing any hepatic dysfunction due to PN/IFE use. By administering Omegaven™ in place of conventional phytosterol/soybean fat emulsions we may reverse or prevent the progression of PN associated cholestasis and thus allow the patient to be maintained on PN until they are able to ingest adequate nutrition enterally.

All patients in the Intestinal Rehabilitation Program at UNMC with an abnormal serum bilirubin (>2mg/dL), receiving PN and not meeting an exclusion criteria will be approached for enrollment. Upon enrollment, the PN lipid source will be switched to Omegaven, and patients will continue to be followed in standard fashion for ongoing intestinal rehabilitation. Patients will continue to have regular follow-up including laboratory evaluation at least once weekly, with periodic radiologic and endoscopic evaluation as per our standard of care. As hypertriglyceridemia is a possible side effect of Omegaven, weekly triglyceride levels will be added to regular labs. Patients will be continued on Omegaven until weaned from intravenous lipids per standard of care. Clinical data will be collected prospectively and will be compared with historical controls.

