### Efficacy and Safety Variables

The efficacy and safety variables in this study will be the change from the baseline assessment to the end of follow-up assessment or end of treatment assessment for the variables listed below. The variables will be determined from: the measurement of body weight, the recording of TPN prescriptions, blood and urine analyses, radiology reports, GI exams, and possible liver biopsies.

- Parenteral Nutrient Requirements (determined from the TPN/PN prescription)
  - TPN/PN infusions (days/week)
  - TPN/PN fluid volume (cc/week)
  - TPN calories (kcal/week)
  - TPN protein (g/week)
  - TPN lipid (g/week)
  - Intravenous vitamins (type and # of infusions/week)
  - Intravenous trace elements (type and # of infusions/week)
  
- Assessment of Nutritional Status
  - Body Composition
  - Body Weight
  
  - Nutrient and Metabolic Profile (Blood analyses)
  - Vitamins- A, B12, C, D, E, folate
  - Minerals and trace elements - calcium, phosphorus, iron, selenium, zinc
  - Serum Proteins - total protein, albumin, globulin
  - Lipid profile - essential fatty acids levels
  - Citrulline, D-lactic acid
  - Serum Electrolytes – (sodium, potassium, chloride, bicarbonate, magnesium)
  
- Assessment of Hydration Status/ Renal Function (Blood analyses)
  - Blood urea nitrogen
  - Serum creatinine

- Assessment of Liver Function (Blood analyses)  
Total bilirubin, direct and indirect bilirubin, alkaline phosphatase, SGOT, SGPT, LDH.
- Assessment of Upper and Lower GI tract/Liver  
Upper and Lower endoscopy, mucosal biopsies and bacterial cultures  
Ultrasound of abdomen/Small bowel follow through, Barium enema  
Liver biopsy (based on clinical indication)

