#### **2. Evaluation**

During this period, the Investigator will evaluate to confirm eligibility. All these procedures are performed at initial evaluation on all patients in the Intestinal Rehabilitation Program, regardless of entry into a study. In addition to a review of body systems, the baseline evaluations will include the recording of body weight and routine urine and blood laboratory analyses. These blood and urine analyses will determine vitamin, trace element, essential fatty acid levels, serum electrolytes, hydration status, kidney function and liver function. Patients will also have radiology and GI exams. It is possible the evaluation may include a liver biopsy. The patient's pre-study TPN prescription will also be recorded.

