#### **4. Treatment/Follow-up Period**

During the follow-up period, patients will continue to be followed by the Intestinal Rehabilitation Program per our standard care for any patient on PN: All patients in IRP are followed with regular blood work, including CBC/diff and CMP at least weekly initially, and in most cases 2-3 times per week. Based on clinical progress, the frequency of laboratory evaluation may be reduced, but is rarely less than once weekly until patients are stable and off PN. These procedures and tests would continue to be performed.

In addition to standard nutritional monitoring, essential fatty acids and serum triglycerides levels will be sent monthly. If a patient should experience lipid intolerance, then serum lipid profiles, including triglycerides, will be sent weekly for the first 4 weeks of therapy, and if stable will be reduced to every two weeks. This monitoring is additional to what would be standard in this population. Any adverse experiences will be recorded for every patient throughout the entire enrollment of the study.

Patients will remain on Omegaven™ until weaned from PN and may continue monotherapy with Omegaven™ as an additional source of calories after the dextrose/protein portion of PN is discontinued.

Upon returning home, patients will be returned to the care of the physician who referred them for participation in the study. Arrangements will be made with the patient's primary care physician to continue usual follow-up. Patients will initially be seen by their primary care physician within one week of returning home.

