### **Monitoring and Possible Dose Reductions**

In addition to standard nutritional monitoring, essential fatty acids will be sent monthly and serum triglyceride levels will be sent weekly. If lipid intolerance develops, defined as serum triglyceride levels > 200 mg/dL, the following will be considered prior to reducing the dose:

- a) If the level was obtained while the patient was receiving a continuous 24- hour infusion of Omegaven™, the total dose will be infused over 20 hours, and a repeat serum triglyceride level obtained prior to resuming the infusion 4 hours later.
- b) Other sources of lipid intolerance will be considered and addressed (drugs, renal disease)

If the triglycerides continue to remain high despite the aforementioned interventions, a dosage reduction of 25% of the current dose will be considered.

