## Statistical Analysis

Data from the two sets of patient population will be pooled and compared (i.e., current protocol patients prescribed Omegaven™ PN compared to historical controls where parenteral lipid calories were provided exclusively through soybean-based formulations). Potential for effect in different patient populations will be minimized by matching patients enrolled in the Omegaven™ protocol to historical controls. Frequency matching will be utilized given the difficulty of paired matching in this patient population. Specific matching criteria will include gender, age, etiology of short bowel syndrome, and severity of liver disease (parenteral nutrition- associated liver disease).

Continuous data will be expressed as mean +/- SEM. A two-way repeated measure ANOVA will be used to compare differences in the two groups with respect to changes between the Evaluation assessment and the subsequent analyses performed at Treatment and Treatment/Follow-up Assessments. Incidence of adverse events in each treatment arm will be compared using Fisher's exact test. Univariate and multivariate analysis will be used to identify baseline factors that may influence outcome. A P-value <0.05 will be considered statistically significant.

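### Follow-up essential fatty acids and triglycerides are tests added for the Omegaven cohort, so the two-group analyses should not compare them with historical controls

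*Combined protocol and SAP*

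**What the plan says.** Under 4. Treatment/Follow-up Period, standard follow-up for programme patients is described as "All patients in IRP are followed with regular blood work, including CBC/diff and CMP at least weekly initially". The next paragraph adds to this: "In addition to standard nutritional monitoring, essential fatty acids and serum triglycerides levels will be sent monthly". After a sentence on closer lipid testing in patients with intolerance, it says: "This monitoring is additional to what would be standard in this population". The Abstract says "weekly triglyceride levels will be added to regular labs", and Monitoring and Possible Dose Reductions says "In addition to standard nutritional monitoring, essential fatty acids will be sent monthly and serum triglyceride levels will be sent weekly".

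Efficacy and Safety Variables lists "Lipid profile - essential fatty acids levels" among the variables to be analysed as change from baseline. Treatment/Follow-up Assessments repeats the nutritional-status block that contains EFA. For baseline, 2. Evaluation includes EFA and says "All these procedures are performed at initial evaluation on all patients in the Intestinal Rehabilitation Program, regardless of entry into a study".

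Statistical Analysis then states: "A two-way repeated measure ANOVA will be used to compare differences in the two groups with respect to changes". The changes run from Evaluation to the later assessments, and the two groups are the Omegaven cohort and frequency-matched historical controls. The same section compares adverse-event incidence with Fisher's exact test. It does not limit either comparison to tests done routinely in both groups. It gives no source or schedule for control laboratory values and no rule for missing ones.

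**The concern.** A comparison with historical controls needs the variable to have been collected in much the same way in both groups. Here the protocol itself says that two follow-up tests belong to the study and not to usual care. A control may have an EFA value from initial evaluation, but nothing in the documents gives that control a scheduled later one.

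Two results are at stake. The first is the EFA change comparison. Without control follow-up values it cannot be run. If a few controls have values, a complete-case analysis silently keeps only those whom someone chose to test. The second is the adverse-event comparison. A raised triglyceride level is found only if triglycerides are measured, and only the Omegaven cohort is measured on a schedule. Matching on gender, age, cause of short bowel and liver-disease severity corrects neither problem.

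**Working it through.** The documents give no figure to reproduce: the cohort size of 100 has no derivation, and the number of controls is not stated. The check is a cross-reading, followed by illustrations whose inputs are assumptions.

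**1. Is the follow-up testing outside standard care?** Three places say so: the Abstract (triglycerides), 4. Treatment/Follow-up Period (both tests) and Monitoring and Possible Dose Reductions (both tests). The standard follow-up tests that are named are a blood count and a metabolic panel.

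**2. Which two-group analysis does each test reach?**

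| | EFA | Triglycerides |
|---|---|---|
| In Efficacy and Safety Variables | yes | no |
| In Evaluation Assessments | yes | no |
| Measured later | yes, via the nutritional-status block and monthly tests | yes, in the treatment and outpatient chemistry lists and the added tests |
| Change from Evaluation defined | yes | no |
| Route into a two-group test | ANOVA | Fisher, if a raised value is recorded as an adverse event |

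The Abstract calls hypertriglyceridemia a possible side effect, and adverse experiences are recorded throughout enrolment. The protocol does not say whether a value above 200 mg/dL counts as an adverse event.

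**3. EFA, loss of information only.** Assume 100 controls, a true difference of 0.4 SD, two-sided 0.05, and controls tested at random. If a share f is tested, the standard error rises by √(1/100 + 1/(100f)) / √(2/100). At f = 0.2 this is √0.06/√0.02 = 1.73. Power is 80.7% with all controls tested, and 63.7%, 37.2% and 22.5% with 50%, 20% and 10% tested.

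**4. EFA, selection.** Suppose the tested share f are those with the highest testing propensity, and propensity correlates ρ with the value (signed towards abnormal). The tested controls' mean **level** then shifts by ρ·φ(t)/f, where t is the (1−f) normal quantile. At f = 0.2, φ(0.8416)/0.20 = 1.40, so ρ = 0.2, 0.3 and 0.5 give 0.28, 0.42 and 0.70 SD. Over f from 10% to 50% and ρ from 0.2 to 0.5, the range is 0.16 to 0.88 SD.

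The plan analyses **change**. If propensity correlates ρ₀ with the Evaluation value and ρ₁ with the follow-up value, and the two values have equal SD, the shift in mean change is (ρ₁ − ρ₀)·φ(t)/f. At f = 0.2:
- ρ₀ = ρ₁ = 0.3: 0 × 1.40 = 0
- ρ₀ = 0.2, ρ₁ = 0.5: 0.3 × 1.40 = +0.42 SD of level
- ρ₀ = 0.5, ρ₁ = 0.2: −0.3 × 1.40 = −0.42 SD of level

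Selection can therefore cancel or bias the change comparison either way, depending on why controls were tested. The level shifts are not estimates of the bias in the planned analysis.

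**5. Triglycerides in Fisher's test.** Assume 100 per group, the same true rate p in both, all Omegaven cases detected and a fraction d of control cases detected. P(Fisher P<0.05) is the sum of Bin(a; 100, p) × Bin(b; 100, pd) over all pairs (a, b) that Fisher's test calls significant.

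| True rate p | d = 1 | d = 0.5 | d = 0.2 |
|---|---|---|---|
| 10% | 2.9% | 19.0% | 58.7% |
| 20% | 3.3% | 44.4% | 93.6% |
| 30% | 3.5% | 66.9% | 99.5% |

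At p = 20% the expected detected cases are 20 for Omegaven against 20, 10 and 4 for controls (100 × 0.20 × d). Here the direction is clear: Omegaven looks worse.

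**The case against.** The strongest objection is that no document describes what controls had measured. The standard blood work is introduced as an inclusive list, not a closed one. The programme measures EFA at initial evaluation, so it may have repeated it. The sentence "This monitoring is additional to what would be standard in this population" directly follows the one on closer testing after intolerance and might refer only to that. This stands in part: the absence of control values is an inference. The narrower reading of that sentence does not remove the problem, because the opening of the same paragraph, the Abstract and the dose-reduction section independently place routine follow-up testing outside standard monitoring.

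A reader might infer that the gap makes Omegaven look better or safer, because only abnormal controls were tested. The documents do not support this. That controls were tested for cause is an assumption, the change-score shift can have either sign, and in the adverse-event comparison the imbalance works against Omegaven.

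A reader might also treat triglycerides as a planned change-from-baseline comparison alongside EFA. They are not: neither the variable list nor the Evaluation list names them.

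Finally, the reach is limited. The primary objective concerns small bowel transplantation, and the hypothesis is judged on liver enzymes and bilirubin, none of which depends on the added tests. That stands in full.

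**Conclusion.** The point holds for two secondary or safety comparisons. As written, the plan puts EFA change into a two-group ANOVA for which controls probably lack scheduled follow-up values. The result would be unworkable or selected, with bias whose size and direction cannot be known from the documents. The plan also leaves open a Fisher comparison in which triglyceride events are sought on a schedule in one group only. That would inflate the Omegaven incidence: under the assumptions shown, the chance of a spurious P<0.05 at a true rate of 20% rises from about 3% to between 44% and 94%.

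The conclusion assumes that controls received the standard monitoring the protocol describes and, for the Fisher part, that raised triglycerides are recorded as adverse events. The numbers of controls, the shares tested and detected, and the correlations are all illustrative. The plan should be corrected before analysis, but the defect does not touch the transplantation outcome or the liver tests.

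**What to change.** In Statistical Analysis:

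- Exclude follow-up EFA and triglycerides from the two-group ANOVA.
- Exclude events detected only by triglyceride testing from the Fisher comparison.
- Report both within the Omegaven cohort: EFA as change from Evaluation; triglycerides as values over time and as the proportion above the protocol's 200 mg/dL definition. Triglycerides have no listed Evaluation value, so a change from Evaluation is not defined for them.
- State how many controls have follow-up values of each test. This also settles the factual question left open above.
- Leave the transplantation, liver-test, parenteral-nutrition-requirement and other standard-care comparisons unchanged. Vitamins, trace elements and similar tests are nowhere called additional and need not be dropped.

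The scheduled triglyceride frequency also differs between sections: monthly in 4. Treatment/Follow-up Period, weekly in the Abstract and in Monitoring and Possible Dose Reductions. These must be reconciled, since frequency determines how many raised values are found.

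The cost is a few sentences and a count from existing control records, with no new patient data. The downside is losing a between-group P-value for these tests, which could not have been interpreted.

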#### **Measurements and Evaluations**

The following assessments will be performed at Evaluation, during the Treatment and Treatment/Follow-up Periods

#### **Evaluation Assessments**

- Parenteral Nutrient Requirements (determined from the TPN/PN prescription)
  - TPN/PN infusions (days/week)
  - TPN/PN fluid volume (cc/week)
  - TPN calories (kcal/week)
  - TPN protein (g/week)
  - TPN lipid (g/week)
  - Intravenous vitamins (type and # of infusions/week)
  - Intravenous trace elements (type and # of infusions/week)

- Assessment of Nutritional Status
  - Body Composition
  - Body Weight
  - Nutrient and Metabolic Profile (Blood analyses)
  - Vitamins- A, B12, C, D, E, folate
  - Minerals and trace elements - calcium, phosphorus, iron, selenium, zinc
  - Serum Proteins - total protein, albumin, globulin
  - Lipid profile - essential fatty acids levels
  - Citrulline, D-lactic acid
  - Serum Electrolytes – (sodium, potassium, chloride, bicarbonate, magnesium)
- Assessment of Hydration Status/ Renal Function (Blood analyses)
  - Blood urea nitrogen
  - Serum creatinine
- Assessment of Liver Function (Blood analyses)
  - Total bilirubin, direct and indirect bilirubin, alkaline phosphatase, SGOT, SGPT, LDH.
- Assessment of Upper and Lower GI tract/Liver
  - Upper and Lower endoscopy, mucosal biopsies and bacterial cultures
  - Ultrasound of abdomen/Small bowel follow through, Barium enema
  - Liver biopsy (based on clinical indication)
- Vital Signs
- Baseline Signs and Symptoms
- Physical Examination
- Total 24-hour oral/enteral intake
- Total 24-hour urine and stool volumes

### Treatment Period

- Vital Signs (daily)
- Signs and Symptoms, daily
- Daily TPN/PN intake
- Total 24-hour oral/enteral intake
- Total 24-hour urine and stool volumes

- Clinical Chemistries - (to include any or all or the following at the discretion of the investigator, 1 or more times per week based on the clinical status of the patient):
  - Blood urea nitrogen (BUN)
  - Creatinine
  - Electrolytes (sodium, potassium, chloride, bicarbonate, magnesium)
  - Calcium
  - Phosphorus
  - Serum amylase
  - Total Protein
  - Albumin
  - Triglycerides
  - Liver function (total bilirubin, direct and indirect bilirubin, alkaline phosphatase, SGOT, SGPT, LDH)

#### **Extended Outpatient Treatment Period (PN Treatment Outpatient)**

- Weight (daily)
- Daily TPN/PN intake
- Clinical Chemistries - (to include any or all or the following at the discretion of the investigator, once per week:
  - Blood urea nitrogen (BUN)
  - Creatinine
  - Electrolytes (sodium, potassium, chloride, bicarbonate, magnesium)
  - Calcium
  - Phosphorus
  - Serum amylase
  - Total Protein
  - Albumin
  - Triglycerides
  - Liver function (total bilirubin, direct and indirect bilirubin, alkaline phosphatase, SGOT, SGPT, LDH)

#### **Treatment/Follow-up Assessments**

- Parenteral Nutrient Requirements (same as the Evaluation Period)
- Assessment of Nutritional Status (same as the Evaluation Period)
- Assessment of Hydration Status/ Renal Function (same as the Evaluation Period)
- Assessment of Liver Function (same as the Evaluation Period)
- Parenteral Nutrient Requirements (same as the Evaluation Period)
- Signs and Symptoms

## **Inclusion Criteria**

The first 100 eligible patients must meet the conditions listed below:

- Patients must be enrolled in the Intestinal Rehabilitation Program at the University of Nebraska Medical Center, and:
- Be unable to meet nutritional needs solely by enteral nutrition and be expected to require PN for at least another 30 days
- Have clinical evidence of parenteral nutrition associated liver disease (PNALD) as defined as direct bilirubin of 2mg/dl or more. A liver biopsy is not necessary for treatment.
- Signed patient informed consent.

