## STUDY PROTOCOL

### Hypothesis

Established parenteral nutrition (PN) associated liver disease can be reversed or its progression halted by using a parenteral fat emulsion prepared from fish oil as measured by normalization of serum levels of hepatic enzymes and bilirubin.

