### **Side Effects (that may lead to Disruption or Discontinuation of Omegaven™):**

The infusion of Omegaven™ can lead to prolonged bleeding time and an inhibited platelet aggregation. The administration of Omegaven™ should be stopped or reduced if there is a marked increase in blood glucose levels during infusion. Undesirable effects that are seen during infusion of Omegaven™ that may also occur with conventional fat emulsions (i.e., Intralipid) include:

Slight rise in body temperature, Heat sensation and/or cold sensation, Chills, Dyspnea, Flushing or cyanosis, Lack of Appetite, nausea, vomiting, Headache, pain in chest, bone pain, Priapism, Increase/decrease in blood pressure, Anaphylactic reactions/erythema

Other expected adverse events that are common to all patients with short bowel syndrome, regardless of the type of fat emulsion they receive, include blood stream infections and re-admittance to hospital. Causes for re-hospitalization include dehydration, bloodstream infections, electrolyte abnormalities, bowel obstruction, and central venous catheter malfunction.

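### The direct bilirubin that qualifies a patient can also be the baseline, so regression to the mean can inflate the apparent fall in the secondary liver outcomes

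*Combined protocol and SAP*

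**What the plan says.** All references are to the combined protocol and SAP.

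- **Hypothesis:** "Established parenteral nutrition (PN) associated liver disease can be reversed or its progression halted", judged by hepatic enzymes and bilirubin becoming normal.
- **Objectives:** the primary objective is need for small bowel transplantation. Improvement in clinical measures of liver disease is secondary.
- **Inclusion Criteria:** patients must "Have clinical evidence of parenteral nutrition associated liver disease (PNALD) as defined as direct bilirubin of 2mg/dl or more". Also, "A liver biopsy is not necessary for treatment". The criterion on parenteral nutrition looks forward only: "Be unable to meet nutritional needs solely by enteral nutrition and be expected to require PN for at least another 30 days". No second value, interval or persistence is stated.
- **Abstract:** patients "with an abnormal serum bilirubin (>2mg/dL), receiving PN and not meeting an exclusion criteria will be approached for enrollment". This does not name the bilirubin fraction and uses a strict inequality. It does not ask for a repeat either.
- **Study Design, 2. Evaluation:** eligibility is confirmed and the baseline laboratory tests are done in this one period.
- **Efficacy and Safety Variables:** efficacy is change from the baseline assessment, and the list includes total and direct bilirubin.
- **Statistical Analysis:** a two-way repeated measures ANOVA compares the groups on "changes between the Evaluation assessment and the subsequent analyses performed at Treatment and Treatment/Follow-up Assessments". Historical controls are frequency-matched on sex, age, cause of short bowel and severity of liver disease. The plan does not say how severity is measured, on what date, or whether controls must meet the 2 mg/dL rule.

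**The concern.** If one measurement both admits the patient and starts the change score, its upward error is built into the baseline. Later values lack that error, so bilirubin falls on average with no treatment effect at all. In the Omegaven cohort alone, this fall cannot be told apart from a drug effect.

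The control comparison removes the artefact only if controls carry the same built-in error. If their baselines are ordinary chart values, the Omegaven group regresses and the controls do not, and the difference is credited to Omegaven. What is at stake is the reading of the secondary liver measures, which are also the measure named in the hypothesis.

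**Working it through.** **No plan figure to reproduce.** The only design number is the enrolment of 100. No SD, effect size, event rate or number of controls is given, so every parameter below except the threshold and the 100 is an assumption.

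**Formula.** Let log direct bilirubin be normal with total SD s and correlation ρ between any two values of one patient, with no drug effect. Select patients whose first value is at least 2 mg/dL. Then

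- a = (ln 2 − ln median) / s
- mean fall on the log scale = (1 − ρ) · s · φ(a) / (1 − Φ(a))
- percentage fall in geometric mean = 1 − exp(−log fall)

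**Set 1: s = 1.0, ρ = 0.7, 0.8, 0.9.** These correlations imply a within-patient CV of about 59%, 47% and 32%, from √(exp(1 − ρ) − 1). The last column was simulated with 2,000,000 draws per scenario.

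| Pool median (mg/dL) | a | φ(a)/(1 − Φ(a)) | Untreated fall (ρ = 0.7 / 0.8 / 0.9) | Next value below 2 mg/dL |
|---|---|---|---|---|
| 1 | 0.693 | 1.285 | 32% / 23% / 12% | 40% / 33% / 23% |
| 2 | 0 | 0.798 | 21% / 15% / 8% | 25% / 20% / 14% |
| 3 | −0.405 | 0.559 | 15% / 11% / 5% | 18% / 14% / 10% |
| 5 | −0.916 | 0.320 | 9% / 6% / 3% | 10% / 8% / 6% |

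For example, at median 1 and ρ = 0.7: 0.3 × 1.285 = 0.386, and 1 − exp(−0.386) = 32%.

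**Set 2: a wider grid.** Medians 1.5, 3 and 5 mg/dL; between-patient log SD 0.6 or 0.9; within-patient CV 20%, 35% or 50%. With within-patient log variance v = ln(1 + CV²), the log fall is (v/s) · φ(a)/(1 − Φ(a)).

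- Highest (median 1.5, SD 0.6, CV 50%): v = ln 1.25 = 0.223, s = √(0.36 + 0.223) = 0.764, a = 0.377, ratio 1.052. Log fall 0.307, or 26%.
- Lowest (median 5, SD 0.6, CV 20%): v = ln 1.04 = 0.039, s = 0.632, a = −1.450, ratio 0.150. Log fall 0.009, or 1%.
- By median: 4% to 26% at 1.5, 2% to 13% at 3, and 1% to 7% at 5 mg/dL. Over the grid, 2.7% to 38% of patients are below 2 mg/dL at the next draw.

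**Chance of a significant result with no drug effect** (Set 2, normal approximation, two-sided 0.05, counting only results in the direction of a fall, for which about 0.025 would be expected with no artefact):

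- Within-cohort test, n = 100: 0.05 to 1.00.
- Against 100 controls (number assumed) not selected on a high value: 0.04 to 0.92.
- Against controls who enter by the same rule with the same baseline definition: the expected regression is equal in both groups and cancels.

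**Checks on possible remedies** (no drug effect):

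- Select on the first value, take a new sample as baseline: mean spurious change about 0% in every scenario. This assumes that fluctuations in the two samples are independent; samples drawn very close together would share some of them.
- Require two values of at least 2 mg/dL and use the second as baseline: a fall of 5% to 22% remains in Set 1 at medians 1 to 2 mg/dL, and 0.6% to 19% in Set 2.

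**The case against.** **The analysis is between groups.** Historical controls matched on liver disease severity would show the same regression if selected and dated alike. This stands as a limit on the claim. A reader might infer that the bilirubin fall will look like reversal by Omegaven; the documents do not support that certainty. They leave the control rule open, so the bias is possible but not established.

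**The plan does not say that one value suffices.** The Screening step collects documentation before Evaluation, which then confirms eligibility, so a two-step check is conceivable. However, the text does not say that the documentation includes bilirubin, nor that the baseline differs from the qualifying sample. The overlap is permitted, not prescribed.

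**The size may be small.** This stands. If most patients are well above 2 mg/dL, the fall is a few per cent. Moreover, falling below 2 mg/dL is not the normalisation named in the hypothesis, for which no cut-off is given. The calculation covers neither normalisation nor enzymes.

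**Temporary cholestasis.** A reader might infer that infection raises bilirubin at entry and then clears. The Side Effects section says only that expected adverse events "include blood stream infections and re-admittance to hospital". It does not describe patients at entry or link infection to bilirubin. The point therefore rests on regression to the mean, which needs no such link.

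**Reach.** It might also be inferred that the main result is biased. The primary objective is transplantation, which has no bilirubin baseline, so the artefact does not act on it directly.

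**Conclusion.** The point holds as a risk to the secondary liver outcomes and to the measure named in the hypothesis. The plan allows the selecting value to be the baseline, and nothing in it secures equal treatment of controls. The untreated fall ranges from negligible to about a third, depending mainly on how close the patient pool lies to 2 mg/dL and how much repeat values vary; the documents give neither. In the group comparison the artefact ranges from nil, with identically selected controls, to the full within-cohort amount, with controls not selected on a high value. It should be corrected because the correction is cheap, but it does not undermine the trial's primary question.

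**What to change.** Keep the entry threshold, and make these changes in Efficacy and Safety Variables and in Statistical Analysis:

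1. Define the liver baseline as a pre-dose sample separate from and after the qualifying value, or the mean of such samples. It can be drawn with routine blood work, as late as practicable before the first infusion.
2. Require controls to meet the same 2 mg/dL rule at a comparable index date, namely entry to or evaluation in the programme, with their next value as baseline. Do not index controls at their first-ever crossing, which could set earlier disease against later disease. Reconcile the bilirubin wording of the Abstract and the Inclusion Criteria first, so that one rule can be applied to both groups.
3. Do not add a subset of patients whose baseline is still at least 2 mg/dL as a ready answer for established disease, because it selects on the baseline again. Use it only against controls selected identically, or with a further baseline sample.
4. State that a separate baseline does not remove cholestasis that later resolves on its own, so a fall within the cohort is not to be read as a drug effect.

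**Cost:** a few sentences and one direct bilirubin on blood that section 4, Treatment/Follow-up Period, says is taken at least weekly at first "and in most cases 2-3 times per week". Controls with only one pre-index value drop out of the liver comparison, and the apparent fall becomes smaller.
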